9.4.2 ANALYSIS OF THE PRIMARY EFFICACY ENDPOINT(S)

NPRS at 4 weeks will be analyzed with Mann-Whitney U-test for between-group comparison. Participants with missing data or lost to follow-up will be excluded from analysis.

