1.2 SCHEMA

1.3 SCHEDULE OF ACTIVITIES (SOA)

Procedures	Screening Day -7 to -1	Enrollment/Baseline Visit 1, Day 0	Questionnaire #1 Day 7	Questionnaire #2 Day 14	Questionnaire #3 Day 21	Questionnaire #4 Day 28	Questionnaire #5 Day 35	Questionnaire #6 End of Study, Day 42
Informed consent	Х							
Demographics	Х							
Medical history	X							
Randomization	Χ							
Physical Examination		Χ						
Administer study intervention		Χ	Χ	Χ	Χ	Χ		
Patient-reported outcome measures		х	х	Х	Х	х	Х	Х
Adverse event reporting			Χ	Χ	Х	Χ	Χ	Х

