5 STUDY POPULATION

5.1 INCLUSION CRITERIA

In order to be eligible to participate in this study, an individual must meet all of the following criteria:

1. Provision of signed and dated informed consent form

- 2. Stated willingness to comply with all study procedures and availability for the duration of the study
- 3. Over the age of 18
- 4. Clinically and/or radiographically diagnosed thumb CMC OA
- 5. Reported average pain intensity during activities of daily living between "3" and "8" on the Numeric Pain Rating Scale (NPRS)

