9.1 STATISTICAL HYPOTHESES

• Primary Efficacy Endpoint(s):

Numeric Pain Rating Scale (NPRS) at 4 weeks

• Secondary Efficacy Endpoint(s):

Numeric Pain Rating Scale (NPRS) at 6 weeks Patient Rated Wrist/Hand Evaluation (PRWHE) at 4 and 6 weeks Single Assessment Numeric Evaluation (SANE) at 4 and 6 weeks

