9.2 SAMPLE SIZE DETERMINATION

A sample size of 54 participants (27 in each group, allowing for 10% withdrawals) was calculated to detect an estimated effect size of 1 in NPRS with a power of 0.80 and alpha of 0.05.

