9.4 STATISTICAL ANALYSES

9.4.1 GENERAL APPROACH

Baseline characteristics and all primary and secondary outcome measures will be analyzed using chisquare and Fisher's exact tests for categorical variables, Mann-Whitney U-tests for between-group comparisons of ordinal or continuous variables, and the Wilcoxon signed rank test for within-group comparisons of ordinal or continuous variables, using a 2-sided level of significance of 0.05. A minimally clinical importance difference (MCID) of 2 is established for changes in the NPRS.

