9.4.3 ANALYSIS OF THE SECONDARY ENDPOINT(S)

NPRS at 6 weeks and PRWHE and SANE at 4 and 6 weeks will be analyzed with Mann-Whitney U-test for between-group comparison. Participants with missing data or lost to follow-up will be excluded from analysis.

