9.4.5 BASELINE DESCRIPTIVE STATISTICS

Demographic information such as age and sex will be collected and analyzed using chi-square and Fisher's exact tests for categorical variables and Mann-Whitney U-tests for between-group comparisons of ordinal or continuous variables. Baseline NPRS, PRWHE, and SANE will be analyzed with Mann-Whitney U-tests.

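### The treatment comparisons leave out the scheduled Day 0 scores, and no effect estimate or confidence interval is named to set against the plan's MCID of 2; the tests are valid, and the power lost is conditional.

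*Combined protocol and SAP*

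**What the plan says.** Section 9.1 defines the primary endpoint as a score at a time point: "Numeric Pain Rating Scale (NPRS) at 4 weeks". Section 9.4.2 gives its analysis: "NPRS at 4 weeks will be analyzed with Mann-Whitney U-test for between-group comparison". Section 9.4.3 follows the same pattern: "NPRS at 6 weeks and PRWHE and SANE at 4 and 6 weeks will be analyzed with Mann-Whitney U-test". Neither section names a covariate, a change score, an effect estimate or a confidence interval.

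The Schedule of Activities (Section 1.3) marks the row "Patient-reported outcome measures" at Day 0 and at each weekly questionnaire to Day 42. The only between-group use of the Day 0 scores is in Section 9.4.5: "Baseline NPRS, PRWHE, and SANE will be analyzed with Mann-Whitney U-tests". That compares the arms before treatment. The Wilcoxon signed rank test in Section 9.4.1 is within-group, so it does not compare treatments either.

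Section 9.4.1 also states: "A minimally clinical importance difference (MCID) of 2 is established for changes in the NPRS". No planned analysis refers to this value. Section 9.2 sizes the trial for an "estimated effect size of 1 in NPRS with a power of 0.80" without saying whether the 1 is a raw point or a standard deviation, and it gives no SD.

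**The concern.** Two things are at stake.

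**Precision.** Entry requires "Reported average pain intensity during activities of daily living between" 3 and 8 on the NPRS (Section 5.1), so two participants can start up to 5 points apart. In a trial of 54 to 60 people, part of the spread in week-4 scores may simply reflect where people started. A baseline-adjusted test removes that part and also guards against chance imbalance. The scores it needs are already scheduled.

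**Interpretation.** A Mann-Whitney p-value does not say how large the effect is. A small trial can reach significance with an observed difference well below 2 points. Without a pre-specified estimate and interval, nobody can tell whether a difference of 2 is compatible with the data. An estimate picked after the data are seen is open to selection.

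**Working it through.** **1. The plan's own figure.** Section 9.2 gives 54 participants, 27 per arm allowing for 10% withdrawals. No SD is stated, so 54 cannot be reproduced directly.
- If the effect is 1 point, an SD of about 1.22 fits: n per arm = 2 × (1.22 × 2.802)² = 23.4, so 24; 24/0.9 = 26.7, so 27 per arm and 54 in total.
- If the effect is 1 SD: 2 × 2.802² = 15.7, so 16; 16/0.9 = 17.8, so 18 per arm and 36 in total, not 54.

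The SD of 1.22 is inferred, so I use a range of 1.22 to 2.5. Evaluable numbers are 24 per arm (27 less 10%) or 27 per arm (30 less 10%, from the recruitment target of 60 in Section 5.5).

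**2. What adjustment can buy.** With a linear relation, adjusting for baseline multiplies the residual SD by √(1 − ρ²): √0.91 = 0.95 at ρ = 0.3, √0.75 = 0.87 at 0.5, √0.51 = 0.71 at 0.7. The documents do not give ρ.

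**3. Simulation on the actual scale.** Assumptions: Day 0 NPRS uniform on the whole numbers 3 to 8; week-4 score = control mean + SD × (ρ × standardised baseline + √(1 − ρ²) × error) − effect, rounded and held within 0 to 10; 10,000 runs per cell. Skewed means exponential errors. Each cell shows power in %, Mann-Whitney → rank ANCOVA.

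| Effect, errors, SD, n per arm | ρ = 0 | ρ = 0.3 | ρ = 0.5 | ρ = 0.7 |
|---|---|---|---|---|
| 1 point, normal, 1.22, 24 | 74.6 → 74.4 | 75.3 → 78.7 | 74.2 → 84.5 | 73.7 → 94.2 |
| 1 point, normal, 2.0, 24 | 36.9 → 36.8 | 35.7 → 38.6 | 36.7 → 46.0 | 35.1 → 59.9 |
| 1 point, normal, 2.0, 27 | 40.6 → 40.8 | 41.2 → 44.3 | 40.8 → 51.0 | 39.4 → 66.1 |
| 1 point, skewed, 2.0, 24 | 68.7 → 68.8 | 54.1 → 60.5 | 46.2 → 61.6 | 38.6 → 71.1 |
| 1 SD, normal, 2.0, 24 | 90.7 → 90.3 | 90.4 → 92.4 | 90.0 → 95.8 | 89.6 → 99.3 |

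Over all cells with a 1-point effect (SD 1.22 to 2.5, both error types, both sample sizes), the change in percentage points is −0.5 to +0.4 at ρ = 0, +2 to +7 at 0.3, +7 to +17 at 0.5 and +16 to +33 at 0.7. On the 1-SD reading, Mann-Whitney power is already 89 to 93% and the gain is at most about 10. With no true effect (20,000 runs per cell), type I error was 4.4 to 5.1% for Mann-Whitney and 4.8 to 5.4% for rank ANCOVA.

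**4. Why a rank version, and not change scores.** Under skewed errors a linear ANCOVA test loses 13 to 26 points against Mann-Whitney at ρ = 0 and 7 to 11 at 0.3; the rank version does not. Mann-Whitney on change scores is not a safe substitute: in a separate normal simulation at SD 1.22, ρ = 0.3 and 24 per arm, its power was 0.62, against 0.75 on the week-4 score.

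**5. Why an interval is needed.** These figures are unadjusted t approximations under assumed SDs at 24 per arm, not results of the planned test. The smallest significant observed difference is 2.013 × SD × √(2/24), which is 0.71 points at SD 1.22 and 1.16 at SD 2.0. Two results would both be significant:
- difference 1.0, SD 1.22: 1.0 ± 0.71, a 95% CI of 0.29 to 1.71, which excludes 2;
- difference 1.2, SD 2.0: 1.2 ± 1.16, a 95% CI of 0.04 to 2.36, which includes 2.

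A p-value alone does not separate them.

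**The case against.** The strongest reply is that Mann-Whitney is valid under randomisation, that nothing in the documents contradicts it, and that adjustment is an efficiency preference whose benefit cannot be established. Much of this stands. There is no bias and no inflated error rate. The restriction to NPRS 3 to 8 may also lower the correlation, which favours the smaller gains; the simulation imposes the correlation and so cannot test this. But the change is nearly free: power is essentially unchanged at correlation 0 and rises materially at 0.5 or more. The missing estimate matters at any correlation.

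A second reply is that pairing a rank test with a linear interval sends mixed messages. This also stands. At 24 per arm the two disagreed about significance in about 3 to 7% of simulated trials with normal errors and 4 to 26% with strongly skewed errors. In the skewed case it was mostly a significant rank test beside an interval that included zero. That is more than a marginal nuisance, so the plan must say in advance which result decides.

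A third reply is that the MCID wording about changes, together with the categorical tests in Section 9.4.1, implies a comparison of individual responders. That is a reasonable guess, but no responder endpoint is written.

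**Conclusion.** The point holds as a recommended improvement, not as a validity defect. The planned comparisons leave the Day 0 scores unused, and they give nothing to set against the MCID of 2.

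The interpretive gap follows from the text alone. The size of the power loss does not: it rests on the assumed SD, correlation, error shape and reading of the effect size, and it runs from nil to about 33 percentage points.

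A reader might infer more in three ways, and the documents support none of them:
- **That the primary test is wrong or biased.** It is a valid test of the stated endpoint.
- **That the trial will lose a known and substantial amount of power.** Neither the SD nor the correlation is given.
- **That the MCID shows change from baseline was the intended primary analysis.** Sections 9.1, 9.4.2 and 9.4.3 all name scores at a time point.

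**What to change.** Before unblinded analysis, amend Sections 9.4.1 to 9.4.3 as follows.

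- **Primary test:** rank ANCOVA, regressing the pooled ranks of week-4 NPRS on arm and the pooled ranks of Day 0 NPRS, two-sided 0.05. This test decides significance.
- **Effect size:** the baseline-adjusted mean difference from linear ANCOVA with 95% CI, stated to describe size only.
- **Secondary outcomes:** the same for NPRS at 6 weeks and for PRWHE and SANE at 4 and 6 weeks, each with its own baseline.
- **Sensitivity analysis:** the planned Mann-Whitney test, with a Hodges-Lehmann shift and 95% CI. On whole-number scores this shift moves in half points, so it does not replace the adjusted difference.
- **MCID:** state whether 2 refers to the between-group difference (then read it against the interval) or to individual change (then report per arm the proportion improving by 2 or more points). The responder comparison should be supportive only: at 24 per arm with about 50% responding, its 95% CI is ± 1.96 × √(2 × 0.25/24) = ± 0.28, or 28 percentage points.

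**Cost:** about one paragraph and slightly more analysis work, with no added visit or questionnaire. The change brings an assumed linear relation between ranks, needs a stated rule for a missing Day 0 score, and accepts that the test and the interval will sometimes disagree.

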7.2 PARTICIPANT DISCONTINUATION/WITHDRAWAL FROM THE STUDY

Participants are free to withdraw from participation in the study at any time upon request.

An investigator may discontinue or withdraw a participant from the study for the following reasons:

- Pregnancy
- Significant study intervention non-compliance
- If any clinical adverse event (AE), laboratory abnormality, or other medical condition or situation occurs such that continued participation in the study would not be in the best interest of the participant
- Disease progression which requires discontinuation of the study intervention
- If the participant meets an exclusion criterion (either newly developed or not previously recognized) that precludes further study participation

Subjects who sign the informed consent form, and are randomized and receive the study intervention, and subsequently withdraw, or are withdrawn or discontinued from the study, will not be replaced.

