7.3 LOST TO FOLLOW-UP

A participant will be considered lost to follow-up if he or she fails to complete subsequent weekly questionnaires and is unable to be contacted by the study site staff.

The following actions must be taken if a participant fails to return to the clinic for a required study visit:

- The site will attempt to contact the participant and counsel the participant on the importance of completing the assigned questionnaires weekly and ascertain if the participant wishes to and/or should continue in the study.
- Before a participant is deemed lost to follow-up, the investigator or designee will make every effort to regain contact with the participant.
- Should the participant continue to be unreachable, he or she will be considered to have withdrawn from the study with a primary reason of lost to follow-up.

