9.3 POPULATIONS FOR ANALYSES

The analysis dataset will be an intention-to-treat (ITT) analysis dataset including all randomized participants.

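### Section 9.3 promises an intention-to-treat analysis of everyone randomized, but 9.4.2 and 9.4.3 prescribe complete-case between-group tests, with nothing beyond exclusion for missing data

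*Combined protocol and SAP*

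**What the plan says.** Section 9.3 names one population: "The analysis dataset will be an intention-to-treat (ITT) analysis dataset including all randomized participants". Section 9.4.2 sets a Mann-Whitney U-test of the 4-week NPRS as the primary analysis and adds: "Participants with missing data or lost to follow-up will be excluded from analysis". Section 9.4.3 carries the same sentence for NPRS at 6 weeks and for PRWHE and SANE at 4 and 6 weeks. Exploratory and subgroup analyses are marked not applicable (9.4.7, 9.4.9), and no other section deals with missing scores.

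Losses are foreseen:
- Section 9.2 allows for 10% withdrawals.
- Section 7.2 lists grounds on which the investigator may withdraw a participant, among them "Disease progression which requires discontinuation of the study intervention". Those who were randomized and treated but "subsequently withdraw, or are withdrawn or discontinued from the study, will not be replaced".
- Section 7.3 gives the definition: "A participant will be considered lost to follow-up if he or she fails to complete subsequent weekly questionnaires and is unable to be contacted".

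In the schedule (1.3), randomization falls under "Screening Day -7 to -1", questionnaire scores start at Day 0, and the last column is "Questionnaire #6 End of Study, Day 42".

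**The concern.** Two things are at stake.

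The first is what the primary result is. If even one randomized participant lacks a Day 28 score, the dataset in 9.3 and the rule in 9.4.2 cannot both be followed. The test then compares those who stayed and answered. That comparison is no longer protected by randomization, and nothing in the plan would test how far the answer depends on who left.

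The second is who is in the test. The exclusion is not tied to the score being analysed. The natural reading is endpoint by endpoint. However, the plan excludes people who are lost to follow-up as well as people with missing data. Read literally, a participant with a valid Day 28 NPRS who cannot be reached before Day 42 would leave the Day 28 test too. Two analysts could build different primary datasets from the same text.

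**Working it through.** **1. The sections side by side.** Section 9.3 puts all randomized participants in the analysis. Sections 9.4.2 and 9.4.3 put in all randomized participants minus those with missing data or lost to follow-up. The two sets agree only if nobody is lost. With the 10% of section 9.2, 60 recruited (5.5) leaves 60 × 0.90 = 54, and the calculated 54 leaves 54 × 0.90 = 48.6. The contradiction needs no further arithmetic.

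**2. A scale for the illustrations.** The documents give no SD. Section 9.2 gives 54 participants for an effect size of 1, power 0.80 and alpha 0.05 (two-sided, 9.4.1). Per arm, n = 2(1.96 + 0.84)² × (SD/difference)².
- Standardized effect of 1: n = 15.7, so 16; 16/0.9 gives 18 per arm, 36 in total. This does not give 54.
- One NPRS point with SD 1.22: n = 23.4, so 24; 24/0.9 gives 27 per arm, 54 in total. This does.

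So 54 fits one raw point with an SD near 1.2. Solving with the t-test gives SD 1.21 for 24 completers per arm and 1.29 for 27. I use 1.21, and 2.0 as an assumed wider case.

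**3. Largest shift from loss in one arm only.** If the worst fraction p of a normal distribution is lost, the mean of those kept moves by φ(z)/(1 − p) SD, where z cuts off the upper fraction p.
- p = 0.10 (3 of 30): 0.1755/0.90 = 0.195 SD, which is 0.24 points at SD 1.21 and 0.39 at SD 2.0.
- p = 0.20 (all 6 of 60 losses in one arm): 0.2800/0.80 = 0.35 SD, which is 0.42 and 0.70 points.

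Loss of the worst sham cases counts against the device; loss of the worst device cases counts for it.

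**4. Simulation with no true effect.** Assumptions: 30 per arm, normal scores at baseline and four weeks, adjacent-week correlation 0.6 or 0.8, 3 lost per affected arm, complete-case Mann-Whitney test, 5,000 runs.

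| Loss | Mean bias (SD) | Rejection rate |
|---|---|---|
| Random, both arms | 0.00 | 0.042–0.050 |
| Same moderate pain-related rule, both arms | 0.00 | 0.052–0.061 |
| Exactly the worst Day 28 scores, both arms | 0.00 | 0.074–0.079 |
| Moderate pain-related, one arm | 0.12–0.14 | 0.07–0.08 |
| Worst Day 28 scores, one arm | 0.19 | 0.11 |

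Moderate means loss driven by the Week 3 score, or by a quantity correlated 0.6 with the Day 28 score. In a separate run of 4,000 replicates on rounded 0–10 scores, losing the 6 worst in the device arm and none in sham gave a rejection rate of 0.23.

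**5. Simulation with a true 1-point effect.** Six of 60 are lost by pain whatever their arm (3,000 runs). The sham arm loses 3.8 to 4.5 on average and the device arm 1.5 to 2.2. The complete-case estimate is 0.84 to 0.91 points under moderate rules. Compared with random loss of the same number, power falls from 0.82–0.83 to 0.76–0.80 at SD 1.21, and from 0.41–0.42 to 0.36–0.39 at SD 2.0. If exactly the worst Day 28 scores are lost, the estimate is 0.72 to 0.76 points.

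**The case against.** The plan is open about the exclusion, which stands close after the ITT sentence, and exclusion is itself a prespecified way of handling missing data. The dataset could hold everyone randomized while each test uses those with a score. The trial is short, double-blind and uses a look-alike sham (4.1, 6.1.1). Participants who stop the device stay in follow-up (7.1), and before anyone is declared lost "the investigator or designee will make every effort to regain contact with the participant" (7.3). Recruiting 60 against a calculated 54 leaves room for losses. The same loss rule in both arms gives no mean bias under the null, and if the device works the bias runs toward no effect.

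All of this stands, and it limits the risk. It does not reconcile 9.3 with 9.4.2, settle who enters the Day 28 test, or supply a robustness check.

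A reader might infer more than the documents support:
- *That all efficacy tests are complete case.* The exclusion is attached to the between-group tests; the within-group Wilcoxon tests in 9.4.1 carry no missing-data rule.
- *That a participant randomized at screening may have no score at all.* Inclusion criterion 5 requires an NPRS between 3 and 8, so an eligibility rating should exist. What may be absent is the Day 0 questionnaire.
- *That a complete-case result will be published as ITT.* No section says how the result will be labelled in a report.
- *That 0.195 SD is the limit for 10% overall loss.* It is the limit for 10% of one arm, which is 3 of 60.

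**Conclusion.** The point holds. The primary and secondary between-group tests as written are complete case, not the ITT analysis that 9.3 states. The plan gives no missing-data method beyond exclusion, no missingness assumption and no sensitivity analysis, and it leaves the scope of the exclusion open to two readings.

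Bias is possible, not proven. A shift under the null requires pain-related loss that differs between arms, which the design makes less likely. It is then bounded by about 0.195 SD for 3 of 30 lost in one arm and 0.35 SD for 6 of 30. With a working device, pain-related loss needs no difference in rule between arms to dilute the estimate. These sizes rest on normal scores, assumed correlations and loss rules, and an SD that is either back-solved or assumed. They are not forecasts. The case for changing the text rests on the contradiction and the undefined primary dataset, not on a demonstrated large bias.

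**What to change.** Before unblinding:

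1. Reword 9.4.2 and 9.4.3, for example: *Participants are analysed in the arm to which they were randomized. A participant is omitted from a comparison only if the score for that comparison is absent.*
2. Amend 9.3 so that this analysis is called randomized participants with observed data (complete case), not ITT. Report by arm the numbers randomized, analysed and missing, with reasons.
3. Add a sensitivity analysis that includes all randomized participants. Use the weekly scores already collected (1.3, 8.1), for example in a repeated-measures model or multiple imputation with a stated pooling rule, together with a delta or tipping-point check.

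The check in item 3 is needed because the model assumes missing at random. In the sham-only simulations, against a complete-case analysis with the same baseline adjustment, the model cut the bias from about 0.11 SD to at most 0.007 SD when loss followed the observed Week 3 score. When loss followed the unseen Day 28 score, or a quantity correlated with it, 0.05 to 0.12 SD remained. A model with baseline as a covariate also omits anyone with no post-baseline score, so those participants need imputation or an explicit assumption.

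Making the repeated-measures model primary is optional: it would change the target from ranks to means. The Mann-Whitney test can stay primary if items 1 to 3 are done.

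The cost is document wording and modest analysis work, with no extra patients or visits.

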9.4.3 ANALYSIS OF THE SECONDARY ENDPOINT(S)

NPRS at 6 weeks and PRWHE and SANE at 4 and 6 weeks will be analyzed with Mann-Whitney U-test for between-group comparison. Participants with missing data or lost to follow-up will be excluded from analysis.

9.4.4 SAFETY ANALYSES

Percentage of each adverse event reported will be calculated.

9.4.5 BASELINE DESCRIPTIVE STATISTICS

Demographic information such as age and sex will be collected and analyzed using chi-square and Fisher's exact tests for categorical variables and Mann-Whitney U-tests for between-group comparisons of ordinal or continuous variables. Baseline NPRS, PRWHE, and SANE will be analyzed with Mann-Whitney U-tests.

